## 8. Subject Safety Monitoring

### Monitors for individual subjects during participation in study procedures

The NIH PI will be responsible for the safety of the participants and for monitoring and reporting any unanticipated problems or AEs. The study personnel will closely monitor patient safety during study procedures. Credentialed clinical staff will monitor all contrast-enhanced MRI scans in accordance with NIH NMR Center policies.

Each patient will be contacted within 24-48 hours following the first dose of anakinra to assess tolerability. At each subsequent visit to NIH, prior to dose escalation, tolerability will be assessed; any subject found to meet dose-limiting toxicity criteria, will discontinue treatment and proceed into the off-treatment follow-up phase of the study.

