## 4. Study Design and Methods

### Study overview

Screening will be done under an existing Neuroimmunology Clinic protocol that allows collection of data required for determining eligibility. Prospective participants who meet eligibility requirements will then provide informed consent and undergo baseline procedures. Following training on self-administration of subcutaneous injections, subjects will be started on initial dose of study drug of 100 mg/d. Participants will have a scheduled follow-up phone call at 24–48 hours following the first dose to assess for any adverse reactions or concerns. Subsequent routine assessment of tolerability and safety will be made at the time of scheduled study visits. For the duration of the study, including dose escalation and follow-up phases, participants will undergo assessments at NIH. Telehealth may be used for conducting routine visits to the NIH Clinical Center. Participants will return at weeks 4 and 8, at which time they will undergo clinic visit, lab work, and 7T brain MRI. As long as no treatment-limiting toxicity is encountered (see “safety endpoints,” Section 8.4) AND the study endpoint is not met (see “efficacy study endpoint,” primary outcome, section 9), the dose will be escalated every 4 weeks to a target dose of 300 mg/day, which will be administered for a further 4 weeks. The final on-treatment study visit will be at week 12. At that time, the drug will be discontinued, with off-treatment visits at weeks 16 and 24 (4 and 12 weeks following treatment discontinuation). The study timeline is in **Error! Reference source not found..**

## Fig. 2

- **MRI at week 24 will be done without Gadolinium, unless clinically indicated.**

Should early drug discontinuation occur, either due to dose-limiting toxicity or to achievement of efficacy endpoint, off-treatment follow-up visits will proceed 4 and 12 weeks after treatment interruption. If a 7T scan cannot be obtained within window at any particular study visit, a 3T MRI can substitute. Leftover biological samples will be stored for future analysis.

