***Specific procedures:***

- **Baseline.** The baseline visit (which may occur over a period lasting up to 2 weeks) will include an interview to confirm that eligibility criteria are met, informed consent, urine or serum pregnancy testing for women of childbearing age, 7T MRI, bloodwork (to include clinical laboratory studies required for establishment of baseline values as well as pre-treatment research samples for exploratory outcomes detailed in Section 9), and lumbar puncture (LP, under fluoroscopy if required for scheduling or if judged by the study team to be in the best interest of the participant). We may collect up to 172.8 ml of blood at the screening/baseline visit. Data and samples collected at screening and sufficient for baseline procedures may be used if collected within one month of dosing and if there is no change in clinical history, but they may also be repeated at this time at the discretion of the PI. If the LP is not tolerated, the participant will be withdrawn and replaced. Clinical scales may include, but may not be limited to, Expanded Disability Status Scale (EDSS), MS Functional Composite (MSFC), Symbol Digit Modalities Test (SDMT), and timed up-and-go (TUG).
- **Dosing.** Within one week of completion of baseline procedures, participants will be given their first supply of anakinra, to be self-administered at a dose of 100 mg/day by SC injection. Subjects will be provided with a sharps box to dispose of empty syringes and instructed to keep all used drug vials. After the first dose, participants will be contacted by telephone to assess tolerability. The dose will be escalated by 100 mg every 4 weeks, up to a target dose 300 mg/day, if tolerated well and as long as safety and efficacy end-points are not yet met. Participants will be instructed that missed doses should not be administered as a double dose at the next dosing time point. Participants will be asked to track daily dosage either electronically or in a written format per their preference. They will be provided with a template drug diary which they may opt to use.

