- **Weeks 4, 8, and 12.** At each visit, sharps boxes and empty vials will be collected. Participants will undergo a brief clinical interview/exam, lab work (to include clinical laboratory studies required for safety monitoring such as CBC with differential and blood collection for research purposes as detailed in Section 9, Exploratory Outcome Measures), clinical scales and LP (week 12 only), and 7T MRI (with gadolinium, if not contraindicated). We may collect up to 175 mL of blood at the week 4, week 8, and week 12 visit not to exceed the Clinical Center's policy for limits of blood drawn for research purposes. The window for these visits will be  $\pm 7$  days.
- **Week 16 (or 4 weeks after dosing discontinuation).** Participants will undergo a brief clinical interview, lab work (clinical and research), 7T MRI (with gadolinium, if not contraindicated). We may collect up to 155 ml of blood at the week 16 visit. The window for this visit will be  $\pm 7$  days.
- **Week 24 (or 12 weeks after dosing discontinuation).** Participants will undergo a brief clinical interview, lab work (clinical and research), clinical scales, LP, and 7T MRI (without gadolinium, unless clinically indicated). We may collect up to 175 mL of blood at the week 24 visit. The window for this visit will be  $\pm 7$  days.

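### The 24–48 hour tolerability call follows only the first 100 mg dose; after the steps to 200 and 300 mg/day the first routine check is nominally 28 days later

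*Combined protocol and SAP*

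**What the plan says.** Three places describe the early contact, and they agree.

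- Section 4, Study overview: "Participants will have a scheduled follow-up phone call at 24–48 hours following the first dose to assess for any adverse reactions or concerns".
- Section 4, Specific procedures, under Dosing: "After the first dose, participants will be contacted by telephone to assess tolerability".
- Section 8, Monitors for individual subjects: "Each patient will be contacted within 24-48 hours following the first dose of anakinra to assess tolerability".

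The dose at that time is the starting dose; the overview states that "subjects will be started on initial dose of study drug of 100 mg/d". Specific procedures then sets out the steps: "The dose will be escalated by 100 mg every 4 weeks, up to a target dose 300 mg/day".

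For everything after the call, the overview says: "Subsequent routine assessment of tolerability and safety will be made at the time of scheduled study visits". Section 8 adds: "At each subsequent visit to NIH, prior to dose escalation, tolerability will be assessed". The check at a visit therefore looks back over the dose level just taken. Visits fall at weeks 4, 8 and 12, each with a window of ±7 days, and the drug is stopped at week 12.

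Safety and tolerability are part of the overall goal in the Précis. They are reported through adverse event tables, a secondary outcome in Section 9.

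**The concern.** The starting dose gets a prompt early enquiry; the two doses reached by escalation do not. The reactions that Section 7 lists as common include injection-site reactions (71% on anakinra, of which 73% were mild), headache (12%) and nausea (8%). Mild, brief events of this kind are easily left out of an interview held four weeks later. The steps to 200 and 300 mg/day also bring a new task for the participant: Appendix 4 has the contents of two or three pre-filled syringes transferred into one 3 mL syringe. No contact is scheduled soon after that task begins.

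What is at stake is the completeness of the adverse event record at the higher doses, in a very small cohort. The target dose is the weakest point, because its only routine tolerability check comes at the visit where treatment ends.

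**Working it through.** The plan gives no figure for this point, so there is none to reproduce. The check compares the contact provisions and does date arithmetic.

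**Inputs.** The call comes 1–2 days after the first dose (Study overview; Section 8). Dose steps occur every 4 weeks, at weeks 4 and 8 (Specific procedures). Visits are at weeks 4, 8 and 12, ±7 days (Specific procedures). Enrolment is at most 10, with 5 completers sought (Section 3). I assume that weeks count from the first dose and that each step is taken at its visit.

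**Time from starting a dose to the first routine tolerability contact**

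| Dose level | Starts | First routine contact | Nominal gap | Routine contacts at that level |
|---|---|---|---|---|
| 100 mg/day | day 0 | call | 1–2 days | 2 (call, week 4 visit) |
| 200 mg/day | week 4 | week 8 visit | 56 − 28 = 28 days | 1 |
| 300 mg/day | week 8 | week 12 visit, drug stopped | 84 − 56 = 28 days | 1 |

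**Effect of the windows.** The visit windows are days 21–35, 49–63 and 77–91. The shortest gap is 49 − 35 = 14 days and the longest is 63 − 21 = 42 days; the second step gives the same results (77 − 63 = 14; 91 − 49 = 42). Both extremes need adjacent visits at opposite ends of their windows, so 28 days is the figure to use.

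**Do other provisions fill the gap?**

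- *Diary.* Specific procedures asks every participant to track daily dosage, but the template is optional. Its Comments column (Appendix 3) has no prompt for reactions. The diary is not among the items listed for collection at the week 4, 8 and 12 visits.
- *Reporting by the participant.* Appendix 3 requires missed doses to be reported and Appendix 4 gives a study-team contact. Neither prompts for symptoms on a schedule.
- *Unscheduled visits.* Section 4 allows them, including by telehealth, but someone must first raise a problem.
- *Weekly clinical meetings.* Section 14 has safety discussed weekly, but this adds no scheduled contact with the participant.
- *Stagger of the first participants.* Section 4 requires 4 weeks of dosing in each of the first two before the next is dosed. On schedule, that covers only the 100 mg/day period.

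None of these is a routine tolerability contact after a dose step.

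**Sensitivity of a small table.** With 5 participants at a dose level, one unrecorded reaction moves the observed rate by 1/5 = 20 percentage points; with 10, by 1/10 = 10 points. This shows the leverage of one event. It does not estimate how many would be missed.

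**The case against.** The best case for the plan is that its three statements agree and that a single first-dose call is a coherent choice. The first dose is the first exposure to a drug with a hypersensitivity warning (Section 7) and the first self-injection after training. The protocol does not give that reason, but it is a fair one. It supports keeping the call; it does not explain having none after the dose steps.

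The other side is also right that the difference is one contact. After the first two days, the rest of the 100 mg/day block is ascertained exactly as the later blocks are. Reactions that recur with daily injection can still be reported at the visit.

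A reader might draw four stronger conclusions, which the documents do not support.

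- *Adverse event tables will look flat or falling with dose by construction.* Section 10 plans no comparison across doses. It has safety assessed qualitatively and events set against earlier anakinra data. Under-recording is a risk of unknown size.
- *The tolerability criteria are compromised.* Section 8 defines them by refusal to escalate, asked at each step, or refusal to continue the higher dose, which the participant declares. Section 10 adds the proportion completing full dosing. None depends on the call.
- *The higher doses are new to the drug.* Section 1, Dosing Considerations, cites safe use up to 200 mg/day in rheumatoid arthritis and reports up to 300 mg/day in rheumatological indications. Section 6 gives a labelled NOMID maximum of 8 mg/kg/day, which covers 300 mg/day from 300/8 = 37.5 kg. The doses are new to the participant and above the rheumatoid arthritis dose, no more.
- *All safety information at the higher doses rests on recall.* Laboratory tests, examination and MRI at visits do not, and the participant can contact the team at any time.

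**Conclusion.** The point holds in a limited form. Early, prompted enquiry about tolerability is scheduled at one of three dose levels. The gap to first routine contact is 1–2 days at 100 mg/day and nominally 28 days at 200 and at 300 mg/day, with 2, 1 and 1 routine contacts respectively. At 300 mg/day the only one coincides with the end of treatment.

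The likely consequence is some under-recording of mild or short-lived early symptoms at the higher doses, confined to the adverse event tables. Its size is unknown. The conclusion assumes that participants do not reliably volunteer such symptoms between visits or recount them fully at the next one; the documents neither show nor exclude this. The trial's validity is not threatened. This is an inexpensive improvement to data on a stated goal.

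**What to change.** In the Study overview and Specific procedures (Section 4) and in Section 8, schedule the existing 24–48 hour telephone contact after the first dose at each dose level, using the same questions each time.

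In Section 10, state that adverse events will be tabulated by the dose in force at onset (100, 200 or 300 mg/day, or off drug), with events found at the early calls marked. The table stays descriptive: everyone takes the doses in the same order, so dose and time on drug cannot be separated.

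The cost is at most two more short calls per participant, 2 × 10 = 20 at the enrolment ceiling, by the staff who already make the first call, plus matching edits in three places and one table layout. The recorded event count at the higher doses may rise slightly, and the marking lets a reader see how much of that comes from the calls. The change concerns only what is asked and how it is reported; doses, escalation and stopping rules stay as written.

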### Parameters to be monitored

Parameters to be monitored include vital signs; clinical bloodwork (CBC and chemistry panel to include hepatic panel); neurological exam; brain MRI. Bloodwork will be performed for the purpose of safety monitoring only.

### Toxicity tables/criteria to be used

Toxicity will be assessed according to the most recent version of the [NCI Common Terminology Criteria for Adverse Events \(CTCAE\)](#).

### Criteria for individual subject withdrawal

Patients may be discontinued from the study at the discretion of the Investigator for medical, administrative or non-compliance issues. Pregnancy will constitute reason for individual subject withdrawal. Furthermore, any subject who wishes to discontinue study drug treatment has the right to withdraw from the study at any time and for any reason. Such participants will be asked to undergo a single concluding visit once off treatment, addressing only safety outcomes.

The following specific criteria will be considered dose-limiting toxicity (DLT) and will define criteria for discontinuation of study drug:

- *Tolerability criteria.* At the time of scheduled dose escalation, subjects will be asked if they are willing to initiate the next higher dosing regimen. Refusal to escalate based on poor tolerability will define the tolerability criteria and will constitute reason for withdrawal of individual patients from

the study. Tolerability criteria will further be met if subjects who escalated to the higher scheduled dose refuse to continue taking this dose due to poor tolerability.

- *General safety criteria.* Development of any treatment-related SAE will constitute reason for withdrawal of individual patients from the study.
- *Neurological safety criteria.* An increase in EDSS of  $\geq 1$  point and/or a decline of  $\geq 20\%$  on the 25-foot timed walk or 9-hole peg test (components of the MSFC) will prompt an extra follow up visit at 2 weeks +/- 3 days. The extra follow up visit would include clinical scales assessment, and may include neurological examination and an additional MRI brain and/or spinal cord, per the discretion of the clinician. Any confirmed sustained decline over the 2 clinic visits will constitute a reason for withdrawal of individual patients from the study. Changes will be measured with respect to average scores obtained during the screening phase. Relapses may constitute reason for withdrawal from the study; relationship to the study drug will be determined by the Independent Study Monitor.
- *Imaging safety criteria.* Appearance of new contrast-enhancing lesions or obvious enlargement of existing lesions on any single scan, in the opinion of the study neuroradiologist, will constitute reason for withdrawal of individual patients from the study. While new contrast enhancement could simply be due to the relapsing-remitting nature of this disease, it could also indicate unintended and unexpected exacerbation of CNS inflammation resulting directly or indirectly from modulation of the immune network by the study drug.

The reasons for discontinuation of the study drug will be recorded in the participant's Clinical Center patient file. These subjects will remain in the study and complete follow-up study visits (4 and 12 weeks following dosing discontinuation).

If discontinuation was because of an AE, the participant will be followed until the event is resolved or stabilized. If the discontinuation was because of pregnancy, the participant will be followed until after delivery.

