## Rationale for outcome measures

**7-tesla MRI.** As described in Section 0, 7T MRI can detect iron deposition within activated macrophages/microglia at the edge of chronic active white matter lesions, which are the ultimate target of the therapy studied in this protocol. The availability of this outcome measure makes it possible to assess the effects of novel therapies on such lesions.

Since multiple sclerosis is an inflammatory disease of the nervous system, and active CNS inflammation can only be detected by leakage of gadolinium contrast by MRI, the majority of the scans performed under this protocol will require gadolinium contrast.

**Safety and tolerability.** Safety and tolerability will be assessed through patient interview and logging of adverse events (AEs), as well as by lab work and imaging. Since anakinra has not previously been used in the treatment of multiple sclerosis and it is not known if this drug could unexpectedly exacerbate disease inflammatory activity, safety monitoring by imaging will require gadolinium contrast for all scans under this protocol except the Month 24 post treatment follow-up scan; at this latter time-point, gadolinium will only be administered if clinically indicated.

**Blood and CSF biomarkers.** We will collect blood and CSF samples for exploratory analysis of other potential biomarkers of anakinra's efficacy. Techniques to be used may include (but are not limited to) flow cytometry immunophenotyping and cytokine/protein assessments. Specific molecules to be assessed may include (but are not limited to); IL-1 $\beta$ , IL-1Ra, IL-2, IL-6, IL-10, IL-12, IL-18, TNF, IFN $\gamma$ , IP-10/CXCL10, neopterin, and neurofilament light chain.

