## 3. Subjects

### Description of study populations

This protocol will enroll up to 10 individuals with progressive or stable MS, evidence of chronic active lesions in the white matter (by MRI), and no evidence of new lesion formation in the prior 3 months or clinical relapse in the prior 12 months (by analysis of prior off-protocol MRI scans). We aim to achieve 5 study completers. NIH employees, regardless of their status as subordinates, relatives, or coworkers of investigators, are eligible.

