An MRI evaluations of the brain may be performed at a field strength of 7T, under conditions designated by the FDA as constituting nonsignificant risk under 21 CFR 812.2(b)(1). Unless specifically designated below, MRI scans are performed on FDA-approved scanners and their use conforms to the corresponding FDA labels. Acquisition parameters may be modified within range. These studies may involve software modifications, including research pulse sequences. All research pulse sequences will conform to the FDA's Criteria for Significant Risk Investigations of Magnetic Resonance Diagnostic Devices.

The following non-FDA-approved systems are used in this study under conditions designated by the FDA as constituting nonsignificant risk, with assurances from the manufacturer that all measures found in FDA-approved MRI (Criteria for Significant Risk Investigations of Magnetic Resonance Imaging Devices) are operational:

- MAGNETOM 7T scanner (manufactured by Siemens)

For the purposes of this protocol, research postprocessing software is exempt from the IDE regulations under 21 CFR 812.2(c) because it is noninvasive, does not require an invasive sampling procedure that presents significant risk, and does not by design or intention introduce energy into a subject. It is unavoidable that results obtained with such software will sometimes have diagnostic implications in the context of this study. However, the diagnosis is always confirmed by another, medically established diagnostic product or procedure.

The study is expected to be completed within 30 months of first dosing. Each of the first two participants will complete at least 4 weeks of dosing prior to the next participant being dosed; thereafter, participants may be enrolled and dosed concurrently.

Additional clinical procedures may be ordered at any study visit, or at unscheduled follow-up visits, based on clinical judgment and would be obtained for clinical purposes.

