### Power analysis

Given the previous natural history data, which indicates that only 1 out of 29 individuals experienced subtle changes in the paramagnetic rim over the long term (a period of several years), we would expect that very few to no untreated participants will experience changes in the short time period observed in this study. Thus, even 1 participant experiencing short term changes would potentially be clinically meaningful. Using an estimated null proportion of individuals with lesion changes of 0.01, a cohort of 5 participants achieves 80% power to detect a difference of 0.27 using a one-sided binomial exact test with a significance level of 0.05. The null hypothesis will be rejected if 1 individual experiences at least one lesion change.

Participants who drop out or in whom anakinra is stopped will be replaced, up to the accrual ceiling or until there are 5 completers — whichever comes first.

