## 14. Data and Safety Monitoring

### Data and safety monitor and monitoring plan

Data and safety will be monitored by the Principal investigator and by the Independent Safety Monitor (ISM), [name]. Data collection and participant safety is discussed and monitored on a weekly basis at the NINDS Neuroimmunology Clinic’s clinical care meetings when a subject is actively enrolled. The ISM’s responsibility will be to provide independent medical monitoring in a timely fashion. The ISM will be notified of all SAEs and serious unanticipated problems immediately, but not more than 7 days, after the PI first learns of the event, and will follow them up through resolution. The ISM will evaluate individual and cumulative participant data when making recommendations regarding the safe continuation of the study. Every 3 months, the ISM , [name], will be provided with reports on safety and enrollment as well as all protocol revisions. If no interval data were collected, the monitor will be informed, and a report will not be required. These reports will include information on laboratory tests and all AEs. The ISM will not have direct involvement in the conduct of the study.

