### Criteria for stopping the study or suspending enrollment or procedures

Enrollment will be suspended, until ISM assessment is completed, if 2 participants develop definite or probable treatment-related SAEs. Depending on the nature of the SAEs and their potential relationship to the study medication, the ISM may request additional clinical information and will decide on further action. If the SAEs are determined to be treatment-related, the study will be stopped. In this event, all enrolled participants still receiving treatment will have treatment discontinued and will proceed into the post-treatment follow-up.

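### Imaging dose-limiting toxicities neither suspend enrolment automatically nor clearly trigger prompt notice to the Independent Safety Monitor, and the 4-week stagger does not wait for a read scan

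*Combined protocol and SAP*

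**What the plan says.** Section 1 (Rationale for outcome measures) justifies contrast scanning by a named uncertainty: "it is not known if this drug could unexpectedly exacerbate disease inflammatory activity". Section 4 accordingly schedules gadolinium at weeks 4, 8, 12 and 16 for safety.

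Section 8 (Criteria for individual subject withdrawal) lists four kinds of dose-limiting toxicity (DLT): tolerability, treatment-related SAE, neurological and imaging. The imaging criterion is "Appearance of new contrast-enhancing lesions or obvious enlargement of existing lesions on any single scan", as judged by the study neuroradiologist. It stops drug in that participant. The same paragraph says enhancement may be natural disease activity or an effect of the drug. For relapses, though not for imaging findings, the section adds: "Relapses may constitute reason for withdrawal from the study; relationship to the study drug will be determined by the Independent Study Monitor".

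At study level:

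- Section 14, stopping criteria: "Enrollment will be suspended, until ISM assessment is completed, if 2 participants develop definite or probable treatment-related SAEs". No other event is counted.
- Section 14, monitoring plan: "The ISM will be notified of all SAEs and serious unanticipated problems immediately, but not more than 7 days". Routine ISM reports come every 3 months and are said to include laboratory tests and all AEs. The ISM evaluates individual and cumulative data when advising on continuation. The clinic discusses safety weekly while a subject is actively enrolled.
- Section 10 (Power analysis): "Participants who drop out or in whom anakinra is stopped will be replaced, up to the accrual ceiling", or until there are 5 completers. Section 3 sets the ceiling: "This protocol will enroll up to 10 individuals".
- Section 4 (Study procedures): "Each of the first two participants will complete at least 4 weeks of dosing prior to the next participant being dosed". After that, dosing may be concurrent. Visits at weeks 4, 8 and 12 have a window of 7 days either side.

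**The concern.** The protocol names one specific CNS hazard, asks participants to accept repeated contrast scans to look for it, and treats a single positive scan as enough to stop the drug. It does not say what a second or third positive scan in other participants should lead to. A silent enhancing lesion is not in itself an SAE, because Section 8 lists treatment-related SAEs and imaging findings as separate criteria. The protocol's own remark that enhancement may be natural disease also makes a definite or probable attribution hard to reach in an uncontrolled study. Meanwhile the replacement rule responds to each stopped participant by enrolling another.

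The stagger exists so that early experience can inform the next exposure. If the next participant can start before the first on-treatment scan has been read, or even taken, the stagger gives no protection against the hazard that only the scan can show.

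**Working it through.** **Plan's own figure.** The only computed design figure is the power statement in Section 10. With 5 participants, a null proportion of 0.01 and rejection at 1 or more, the type I error is 1 − 0.99^5 = 0.049. Power at 0.01 + 0.27 = 0.28 is 1 − 0.72^5 = 0.807. Both agree with the stated 5% and 80%, and this point does not depend on them.

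**Reading the rules together.** Take a participant with a silent enhancing lesion on a week-4 scan.

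| Step | Does the text require it for this event? |
|---|---|
| Stop drug in that participant | Yes (Section 8) |
| Independent judgement of relatedness | Stated for relapses, not for imaging findings |
| ISM notice within 7 days | Only if classed as an SAE or serious unanticipated problem |
| Appears in the 3-monthly ISM report | If recorded as an AE, which is not stated |
| Counts toward suspending enrolment | Only if a definite or probable treatment-related SAE |
| Participant replaced | Yes, up to 10 enrolled or 5 completers |

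The suspension rule has no imaging count. In principle all 10 participants could meet the imaging criterion without reaching it, provided fewer than 2 were classed as definite or probable treatment-related SAEs.

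**How often would repeated events arise?** The documents give no rate, so let p be an assumed probability of an imaging DLT per participant, independent between participants and the only cause of non-completion. Enrolment continues to 5 completers or 10 enrolled.

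- No event has probability (1−p)^5. Exactly one event has probability 5p(1−p)^5, since the event can come at any of five positions before the fifth completer.
- So P(2 or more) = 1 − (1−p)^5 × (1 + 5p). At p = 0.10: 1 − 0.59049 × 1.5 = 0.114.
- Expected numbers dosed come from exact enumeration. Expected events are p times the number dosed.

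| Assumed p | P(2 or more) | Expected dosed | Expected imaging DLTs |
|---|---|---|---|
| 5% | 3.3% | 5.26 | 0.26 |
| 10% | 11.4% | 5.56 | 0.56 |
| 20% | 34.5% | 6.24 | 1.25 |
| 30% | 58.0% | 7.06 | 2.12 |
| 50% | 89.1% | 8.77 | 4.39 |

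**Stagger.** Anchor windows to first dose and use the fastest permitted pace.

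- Participant 1 starts on day 0. Four weeks of dosing end on day 28, so participant 2 may start then.
- Participant 1's week-4 scan may fall between day 28 − 7 = 21 and day 28 + 7 = 35, up to 7 days after participant 2 may start.
- Participant 3 may start on day 28 + 28 = 56. Participant 2's week-4 scan falls on days 28 + 21 = 49 to 28 + 35 = 63. Participant 1's week-8 scan falls on days 49 to 63 as well.
- When participant 3 starts, as few as one on-treatment scan may exist: participant 1's week-4 scan, at 100 mg/day.

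This is a permitted bound, not the expected pace. Section 4 allows 30 months for the study.

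**The case against.** The strongest reply is that study-level oversight exists and is not optional. Section 14 has the ISM evaluate cumulative data, requires 3-monthly reports and provides weekly safety discussion. Section 4 (Study overview) promises real-time monitoring, and Section 15 prompt data review. A reader might infer from the suspension rule that nothing requires a study-level review of imaging DLTs; the documents do not support that. What remains is narrower. The review has no imaging trigger, its named content omits MRI findings and DLTs, and a 3-month interval is about one full 12-week course.

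Second, an imaging DLT might qualify as a serious unanticipated problem, or be reportable to the IRB under the policy cited in Section 16, which is not in the documents. That is possible, so the accurate statement is that expedited notice is not clearly triggered, not that it is ruled out.

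Third, a reader might infer that an automatic pause at the second imaging DLT would spare many people exposure. If participants were dosed one at a time, enumeration gives 5.2, 5.1, 4.7 and 3.7 people dosed by the pause or completion at rates of 10%, 20%, 30% and 50%. That is not a fair benefit estimate. Section 4 allows concurrent dosing after participant 2. A simulation at that fastest pace, with five kept in play from day 56 and events equally likely at the three on-treatment scans (an assumption), gives about 5.4 to 5.7. A pause can also be lifted. The higher rates have no support in the documents either: entry criteria exclude recent relapse, new lesions and baseline enhancement, and Section 17 lets disease-modifying therapy continue.

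Fourth, a reader might suppose that everyone from participant 3 to participant 10 could start on day 56. With 5 completers sought, participants 6 to 10 are replacements and enter only after others stop.

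Finally, individual protection is strict: one lesion on one scan stops the drug with no relatedness test. That stands. The gap concerns what other and future participants gain from the finding.

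**Conclusion.** The point holds in a limited form. No number of imaging DLTs automatically suspends enrolment or clearly triggers expedited ISM notice, while stopped participants are replaced up to 10. Imaging DLTs reach study level through weekly clinic discussion and a routine 3-monthly report that does not name them. The stagger can let participant 2 start up to 7 days before participant 1's week-4 scan.

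These statements rest on the text alone. How often they would matter depends on a rate the documents do not give: two or more events in about 3% of trials at 5% per participant, 11% at 10%, 34% at 20% and 58% at 30%, assuming independence and no other reason for stopping. The change should be made because the hazard is the protocol's own and the remedy is cheap. The existing ISM role makes this a missing trigger and timeline, not an absence of oversight.

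**What to change.** 1. In Section 14, add imaging DLTs to the events notified to the ISM within 7 days. Have the ISM judge relatedness, as Section 8 already provides for relapses, and issue a documented recommendation on continuing enrolment and dose escalation when a second participant meets the criterion.
2. In Section 4, dose participants 2 and 3 only after the preceding participant's week-4 scan has been read.
3. In Section 14, list imaging DLTs among the contents of the ISM report, by participant and visit.

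An automatic suspension of enrolment at two imaging DLTs is an option for the sponsor and ISM to weigh. The number 2 would mirror the SAE rule and is not derived. Natural disease activity alone would trigger it in about 3%, 11% and 34% of trials at assumed background rates of 5%, 10% and 20% per participant. With no control group, the ISM could not separate drug effect from natural activity with certainty.

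Cost: protocol wording, faster notice, possibly one extra ISM review, and about a week's delay for each of participants 2 and 3. No additional scan or contrast dose is needed.
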